8.4.6.3 Missed Doses

If a participant misses a dose according to the protocol-outlined schedule, the participant (or caregiver, as applicable) should administer the dose as soon as possible and continue on the original schedule with the exception that 2 doses of medication should not be administered less than 48 hours apart.

8.4.7 Treatment Compliance

Study medication compliance will be monitored periodically using standard drug accountability procedures. Drug accountability will be reviewed by the site study staff at each visit to confirm treatment compliance. If a participant misses 2 consecutive doses (not related to an AE/SAE), site staff will discuss discrepancies with the participant at each on-treatment study visit and counsel the participant of the importance of compliance with the assigned regimen. Participants and/or caregivers (as applicable) may be re-trained in study medication administration, if necessary to address study medication compliance issues. If the participant misses 2 more consecutive doses during the study, the investigator should consult with the medical monitor to determine the appropriate course of action for the continued treatment of the participant, which may include withdrawal of study medication.

8.4.8 Prior and Concomitant Therapy

All medications taken from within 3 months (12 weeks) before the Screening Period until the Week 52/PTFU Visit must be recorded on the eCRF. In addition, medications administered between the Week 52/PTFU Visit and the 6 Month Post PTFU Visit that could potentially

impact bone mineral density assessments, as well as other therapies for NASH whether approved or investigational, will be recorded on the eCRF.

Prior medications are defined as medications taken prior to the first dose of study medication and discontinued before the first dose of study medication. Concomitant medications are defined as any medication taken after the first dose of study medication until the Week 52/PTFU Visit. Concomitant medications (e.g., prescription, over-the-counter, or herbal) should be administered during the study only if they are prescribed for treatment of specific clinical events.

Restrictions and prohibitions on prior and concomitant medications are described in [Section 8.3.7](#).

8.4.9 Treatment After the End of the Study

At the end of the study, the sponsor will not continue to provide sponsor-supplied study medication to participants/investigators unless the sponsor chooses to extend the study. The investigator should ensure that each participant receives appropriate standard of care to treat the condition under study.

The sponsor reserves the right to terminate access to sponsor-supplied study medication if any of the following occur: a) the study is terminated due to safety concerns or other reasons; b) the development of BMS-986036 for treatment of NASH or other indications is terminated for other reasons, including but not limited to lack of efficacy and/or not meeting the study objectives; c) the participant can obtain medication from a government-sponsored or private health program. In all cases, the sponsor will follow local regulations.

8.5 Efficacy and Safety Variables

Study procedures and timing are summarized in the Schedule of Activities ([Section 1](#)).

Waivers or exemptions from protocol-required evaluations are not allowed.

8.5.1 Efficacy Assessments

Every effort must be made to ensure that the same evaluator(s) complete the assessment for each participant. If the evaluator(s) is unable to complete the evaluation, then a qualified individual with overlapping experience may perform the evaluation. Documentation of who performed the evaluation is to be recorded in source documents. Assessments should be performed at approximately the same time of day throughout the duration of the study. Baseline assessments must be performed prior to dosing with study medication. Procedures not specified in the protocol that are part of standard care may be performed if they do not interfere with study procedures; any data arising from such procedures are not to be reported in the eCRF.

All efficacy assessments will be completed prior to study medication administration. Participant questionnaires will be administered electronically, and information gathered electronically (i.e., electronic patient-reported outcome) will serve as the source document where possible.

The following procedures or tools will be used to assess participant's disease activity during the study (see the Schedule of Activities in [Section 1](#)):

- Liver biopsy (see [Section 8.5.1.1](#)) submitted to the central pathologist at Screening, and at Week 24 or the ET Visit, if applicable
 - Histological assessments of fibrosis stage and NASH activity
 - Assessments of CPA and fat in stained tissue by morphometry
 - Assessments of fibrosis using digital pathology
- Noninvasive measures of fibrosis and/or cirrhosis
 - Noninvasive scores of hepatic fibrosis (see [Section 8.5.1.2](#)) (AST-Platelet Ratio Index [APRI], Fibrosis 4 [FIB4] Index, Enhanced Liver Fibrosis [ELF] Score, NAFLD Fibrosis Score) at Day 1, Week 24, and Week 48 (or the ET Visit, if applicable)
 - Liver stiffness as determined by MRE (see [Section 8.5.1.3](#)) at Screening, Week 24, and Week 48 (or the ET Visit, if applicable)
- Hepatic fat fraction as determined by MRI-based proton density fat fraction (PDFF; see [Section 8.5.1.3](#)) at Screening, Week 24, and Week 48 (or the ET Visit, if applicable)
- Physical metabolic assessments (see [Section 8.5.1.5](#)) at Screening, Day 1, Week 24, and Week 48 (or the ET Visit, if applicable)
 - Body weight
 - Body mass index (BMI)
 - Waist circumference
- Laboratory Metabolic Assessments (see [Section 8.5.1.5](#)) at Screening, Day 1, Week 24, and Week 48 (or the ET Visit, if applicable)
 - Lipids (LDL, HDL, TGs)
 - Fasting plasma glucose
 - Fasting plasma insulin
 - Hemoglobin A1c
- Exploratory Biomarkers (see [Section 8.5.4](#))
 - Transaminases at each visit through Week 52/PTFU
 - Adiponectin at Day 1, Week 4, Week 8, Week 12, Week 24, Week 48 (or the ET Visit, if applicable) and Week 52/PTFU
 - PRO-C3 at Day 1, Week 4, Week 8, Week 12, Week 24, and Week 48 (or the ET Visit, if applicable) and Week 52/PTFU
- Health-related quality-of-life (HRQoL) questionnaires (see [Section 8.5.1.6](#)) at Day 1, Week 24, and Week 48 (or the ET Visit, if applicable)
 - 3-Level EuroQol 5 Dimension (EQ-5D-3L) questionnaire
 - 36-question Short Form (SF-36) quality-of-life questionnaire

- Chronic Liver Disease Questionnaire-Nonalcoholic Fatty Liver Disease (CLDQ-NAFLD) questionnaire

8.5.1.1 Liver Biopsy

A liver biopsy will be performed during Screening if no liver biopsy specimen collected within 6 months (26 weeks) prior to informed consent is available and readable by the Central Pathologist.

The on-treatment liver biopsy should be performed within \pm 7 days of the Week 24 Visit. However, if a biopsy cannot be scheduled within the window specified above, the biopsy should be performed as close to schedule as possible.

For participants prematurely discontinuing study medication, liver biopsy will be performed at ET Visit if the participant has completed at least Week 20 and has not had a Week 24 biopsy. If a participant discontinues study participation prior to Week 20 they should consider having a liver biopsy at ET.

Histological assessment of the tissue sample will be conducted by a blinded Central Pathologist. The central reader will be a medical doctor, board certified in pathology, with experience in liver pathology in a clinical study setting.

The on-treatment liver biopsy results will remain blinded to site personnel until after the study database is locked; incidental findings of potential clinical relevance (as determined by the medical monitor) from the central pathologist will be provided to the investigator.

Any incidental findings of potential clinical relevance that are not directly associated with the objectives of the study should be evaluated and handled by the investigator per the site's standard of care and clinical judgment.

Liver tissue should be collected using a 16 gauge (or larger) cutting needle (e.g., Bard, Microvasive, or TruCut) whenever possible. Use of suction needles (e.g., Menghini, Jamshedi, or Klatskin) are allowed, but may cause fragmentation of fibrotic specimens and impede the evaluation of fibrosis, and should therefore be avoided, if possible. At least 2 cm length of tissue should be obtained.

Additional details on the acquisition, quality requirements, histological preparation, and shipping of histological samples are in the Central Laboratory Manual and the Central Pathology Manual.

Histological Scoring

NASH CRN

For associated primary and secondary endpoints, the NASH CRN system²⁶ will be used to score the histologic samples and results are reported as the NAFLD Activity Score (NAS) and the NASH CRN Fibrosis Score. The NASH CRN system is based on the concept that necroinflammatory lesions and stage of fibrosis should be evaluated separately; it assesses

liver biopsies for degree of steatosis (0-3), lobular inflammation (0-3), hepatocellular ballooning (0-2), and fibrosis (0-4).

NAS

The 3 categories of steatosis, lobular inflammation, and ballooning scores are added together in an unweighted fashion to determine the NAS, which ranges from 0 to 8 (see Table 7 below).

The NAS should not be considered a replacement for the Central Pathologist's diagnosis of NASH.

Table 7 **NAS Scoring System**

Histology Variable	Grade	Score
Steatosis	< 5%	0
	5%-33%	1
	> 33% - 66%	2
	> 66%	3
Lobular Inflammation ^a	none	0
	< 2	1
	2 - 4	2
	> 4	3
Ballooning	none	0
	few	1
	many	2

NAS = NAFLD Activity Score

^a Foci per x200 field

Fibrosis

NASH CRN Fibrosis

Fibrosis is staged separately from NAS on a 0-4 scale: 0 (none); 1 (perisinusoidal or periportal fibrosis); 2 (perisinusoidal and portal/periportal fibrosis); 3 (bridging fibrosis); 4 (cirrhosis).

Participants will be evaluated for progression to cirrhosis (NASH CRN Fibrosis stage 3 to stage 4) at Week 24.

Ishak

A modified Ishak scoring system will also be used to stage fibrosis in the histologic samples. The Ishak system (0-6 scale) was originally developed to grade portal-based liver fibrosis associated with viral hepatitis.²⁷ The modified Ishak system has been adapted to stage central-based liver fibrosis associated with NASH, and it also uses a 0-6 scale:

- 0: No fibrosis

- 1: centrilobular pericellular fibrosis
- 2: centrilobular and periportal fibrosis
- 3: bridging fibrosis (few bridges)
- 4: bridging fibrosis (many bridges)
- 5: early or incomplete cirrhosis
- 6: established or advanced cirrhosis

Morphometric Analysis of CPA and Fat Percentage in Stained Tissue

There is considerable intra- and inter-individual variation of hepatopathologist assessment of fibrosis stage on liver biopsy. Assessment of CPA is a method by which the amount (percentage) of collagen in stained tissue sections is analyzed using morphometric image analysis. This allows for a quantitative assessment of fibrosis. Percentage of fat in stained tissue sections is also analyzed using morphometric image analysis. These morphometric assessments will be performed by a blinded Central Pathologist. Additional details on these morphometric assessments are in the Central Pathology Manual.

Assessment of NASH and Fibrosis Using Digital Pathology

Liver biopsy samples will be evaluated using digital pathology, which may include automated techniques.²⁸

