8.3.1 Inclusion Criteria

1. Signed written informed consent
 - a) Participants must be willing to participate in the study and sign the informed consent form(s) (ICF[s])
 - b) Participants (and caregivers as applicable) must be willing and able to complete all study-specific procedures and visits
2. Liver biopsy performed within 6 months (26 weeks) prior to the Screening Period. Biopsy performed prior to ICF must be available to the central reader prior to randomization. If historical biopsy is not available, a liver biopsy will be performed during the Screening Period (see [Section 8.5.1.1](#)). Biopsy must be consistent with NASH, with:
 - a) A score of at least 1 for each NAS component (steatosis, lobular inflammation, and ballooning), as assessed by the central reader
AND
 - b) Stage 3 liver fibrosis according to the NASH CRN classification, as assessed by the central reader
3. Participants taking anti-diabetic, anti-obesity, or anti-dyslipidemic medications must have been on stable regimens for at least 3 months (12 weeks) (6 weeks for statins) prior to and during the Screening Period. The investigator may contact the medical monitor regarding the stability of a participant's regimen when determining eligibility for study participation. Participants taking vitamin E at doses ≥ 800 IU/day must have been on stable doses for at least 6 months (26 weeks) prior to and during the Screening Period. Vitamin E treatment (≥ 800 IU/day) must not have been initiated after the qualifying liver biopsy was performed.

4. Age and reproductive status
 - a) Men or women 18 to 75 (inclusive) years of age
 - b) Women of childbearing potential (WOCBP) must have a negative pregnancy test (minimum sensitivity 25 IU/L or equivalent units of human chorionic gonadotropin) within 24 hours prior to the start of study medication
 - c) Women must not be breastfeeding at any time during the study
 - d) WOCBPs must agree to follow instructions for method(s) of contraception for the duration of treatment (BMS-986036 or placebo) plus 5 half-lives of study medication (5 days) plus 30 days (duration of ovulatory cycle) for a total of 35 days after the end of the Double-Blind Treatment Period
 - e) WOCBPs who are continuously not heterosexually active are exempt from contraceptive requirements but must undergo pregnancy testing as described in the Schedule of Activities in [Section 1](#)

[figure not shown]

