6.1.1 Primary Efficacy Analysis

The primary efficacy endpoint is the proportion of participants who achieve a ≥ 1 -stage improvement (as defined by NASH CRN Fibrosis Score) in fibrosis without worsening of NASH or NASH improvement (as defined by NAFLD Activity Score) with no worsening of fibrosis (as defined by NASH CRN Fibrosis Score) at Week 24, as determined by liver biopsy.

For this protocol, improvement in fibrosis is defined as a decrease of fibrosis by ≥ 1 point, as determined by the NASH CRN Fibrosis Score. Worsening of fibrosis is defined as an increase of fibrosis by ≥ 1 point, as determined by the NASH CRN Fibrosis Score. Worsening of NASH is defined as an increase of the

Sponsor: Bristol-Myers Squibb

Protocol no: MB130-068

NAFLD Activity Score (NAS) by ≥ 1 point. NASH improvement is defined as a decrease of NAS by ≥ 2 points (with contribution from > 1 NAS component).

A Cochran-Armitage trend test of proportions at a one-sided 0.05 level of significance will be used to examine the linear trend among the proportions across treatment groups. In addition, 95% confidence intervals (CIs) for the odds-ratio of each BMS treatment group to placebo will be provided. The null hypothesis states that there is no association between treatment groups and fibrosis stage improvement. The alternative hypothesis states that there is an association between treatment groups and fibrosis stage improvement. The Cochran-Armitage trend test does not take into consideration stratification factors into the model therefore, further sensitivity analysis will be performed as described below in SAP Section 6.1.1.1.

The proportion of participants with response will be summarized as frequency counts and percentages by randomized strata as well as overall for each treatment group.

Participants who prematurely discontinue from treatment without a biopsy result for NASH CRN Fibrosis Score or NAS at Week 24 (or ET, if applicable) or otherwise have a missing Week 24 (or ET, if applicable) biopsy result will be considered non-responders for the primary analysis of the primary efficacy endpoint.

The primary analysis will be based on the mITT population. In addition, a completer analysis of the primary variable will be performed. Patients with an evaluable Week 24 biopsy results are considered completers. All biopsy results will be included in the participant listings.

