6.1.1.1 Sensitivity Analyses

There will be a sensitivity analysis of primary efficacy endpoint to determine the effect of the stratification variables Japan, T2DM and NAS using the randomized strata. A sensitivity analysis using an extended Cochran Mantel-Haenszel (CMH) correlation test will be used to assess the trend among the proportions for treatment groups with an adjustment to strata. A two-sided 0.10 level of significance will be used. In addition, logistic regression analysis will be performed to further assess the dose response relationship with treatment groups and stratification factors as main effects.

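### All participants enter at NASH CRN stage 3, and the responder analyses leave the finer baseline fibrosis measures (modified Ishak, CPA) unused; adding one to the supportive logistic model is a cheap improvement

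*Protocol*

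**What the plan says.** Protocol 8.3.1 admits only participants with "Stage 3 liver fibrosis according to the NASH CRN classification, as assessed by the central reader".

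Protocol 8.5.1.1 adds a second scale: "A modified Ishak scoring system will also be used to stage fibrosis in the histologic samples". On it, grade 3 is "bridging fibrosis (few bridges" and grade 4 is "bridging fibrosis (many bridges". The same section describes CPA as a quantitative, image-based measure of collagen. Protocol 8.5.1 sends the Screening and Week 24 biopsies to the central pathologist for fibrosis staging and CPA. The Ishak-improvement and CPA-decrease endpoints in SAP 4.2 cannot be derived without baseline values.

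For the primary endpoint, SAP 6.1.1 states: "A Cochran-Armitage trend test of proportions at a one-sided 0.05 level of significance will be used". It acknowledges the limitation: "The Cochran-Armitage trend test does not take into consideration stratification factors into the model". SAP 6.1.1.1 then plans an extended CMH test to "determine the effect of the stratification variables Japan, T2DM and NAS using the randomized strata", and adds that "logistic regression analysis will be performed to further assess the dose response relationship with treatment groups and stratification factors as main effects". SAP 6.1.2 applies the primary method to all secondary endpoints. Only the exploratory repeated-measures model in SAP 6.4 includes the endpoint's own baseline value alongside the stratification factors.

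**The concern.** The score behind most of the fibrosis endpoints is constant at entry, so it cannot adjust for baseline severity. None of the three randomisation factors measures fibrosis. By the scale's own definitions, the step below Ishak 3 is non-bridging fibrosis and the step above Ishak 4 is early cirrhosis. Few or many bridges could therefore plausibly affect the chance of crossing a CRN boundary by Week 24.

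At stake are the odds ratios of each dose against placebo, which come from arms of about 49. Protocol 6.2.1 says that Phase 3 dose selection will draw on this trial. A chance difference between arms in baseline bridging would pass into those odds ratios, and no planned responder analysis corrects for it.

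**Working it through.** **1. The plan's own figure.** Inputs from Protocol 9.1: rates 15/20/30/40%, 40 per arm, one-sided 0.05. With scores s = 0, 1, 2, 3 (mean 1.5):
- Mean of the trend statistic: Σ n·p·(s − 1.5) = 40 × 0.425 = 17.0
- Null SD: √(0.2625 × 0.7375 × 200) = 6.22
- Alternative SD: √(40 × 0.9194) = 6.06
- Power: Φ[(17.0 − 1.645 × 6.22)/6.06] = 86.8%

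Dose scores 0/10/20/40 give 86.1%. At N = 197 the two figures are 92.3% and 91.7%. The stated minimum of 80% is met without any covariate.

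**2. Stratifying a trend test by Ishak.** The documents give neither the Ishak 3/4 split nor its relation to response. Both are assumed here: an even split and a prognostic odds ratio (OR) from 1 to 5, with arm rates held at the plan's values. There were 60,000 simulated trials per setting.

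| Prognostic OR | 40 per arm: unadjusted → stratified | 49 per arm: unadjusted → stratified |
|---|---|---|
| 1 | 87.2 → 86.8% | 92.5 → 92.3% |
| 2 | 87.2 → 87.5% | 92.5 → 92.8% |
| 3 | 87.0 → 88.2% | 92.5 → 93.4% |
| 5 | 87.3 → 89.9% | 92.4 → 94.3% |

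With 30% or 70% at few bridges, the gain is 0.1 to 0.2 points at OR 2 and 0.6 to 1.2 points at OR 3. Type I error is about 5.1 to 5.2% either way.

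For fibrosis improvement the documents give no rates. At assumed rates of 12/15/21/28% and 49 per arm, one simulation gave 70.7 → 70.7% at OR 2 and 70.5 → 72.3% at OR 4.

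**3. The logistic model itself.** At 49 per arm, trend power in the logistic model moves by about 0 at OR 1, 0.2 to 0.4 points at OR 2 and 1.2 to 2.4 points at OR 4. The standard error of the log odds ratio per dose step goes from 0.156 to 0.159 (OR 2) or 0.165 (OR 4). For 40 mg against placebo, in a model that also carried a non-prognostic CPA term, it goes from 0.525 to 0.538 or 0.556. The interval widens. Power rises because the conditional effect moves further from the null than its standard error grows.

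**4. Chance imbalance.** The SD of the difference in Ishak 3 share between two arms of 49 is √(2 × 0.25/49) = 0.10. A gap of at least 10 points in either direction has a probability of about 32%.

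At the planned 15% against 40%, the odds ratio is (0.40/0.60)/(0.15/0.85) = 3.78. With a prognostic OR of 3 and an even split, the stratum rates are 21.6% and 8.4% on placebo, and 52.8% and 27.2% on 40 mg. A 10-point gap favouring placebo (55% against 45% at few bridges) gives expected rates of 15.7% and 38.7%, and an odds ratio of 3.40. A 20-point gap gives 3.07. A 10-point gap in the other direction gives 4.20. On the log scale, the 10-point shift is ln(3.78/3.40) = 0.106, about 0.2 of the 0.525 standard error.

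**5. Room in the model.** At the assumed fibrosis rates there are 49 × 0.76 ≈ 37 events. Three treatment terms, four for the five strata, Ishak and CPA make nine terms, or about 4.1 events per term. With one added covariate there are eight terms, or about 4.7. For the primary endpoint, 49 × 1.05 ≈ 51 responders over eight terms gives about 6.4.

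**The case against.** The strongest reply is that nothing is broken. The planned power is met, type I error is unaffected, randomisation makes the unadjusted comparison valid, and the 95% intervals already allow for chance imbalance. Secondary p-values are declared descriptive. All of this stands, and it is why the point is only an improvement.

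The prognostic value of Ishak is also undocumented and may be weak. Protocol 8.5.1.1 itself warns of considerable reader variation in fibrosis staging, which would dilute a few-versus-many-bridges covariate. The primary composite can be met through NAS improvement without any fibrosis regression. If Ishak carries no information, adjustment costs a fraction of a point of power. This also stands, and it leaves the size of any gain open.

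The sparse-event objection is sound too. Adding both Ishak and CPA to every endpoint, including progression to cirrhosis, would overload the model. That argues for one covariate per endpoint.

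Two stronger readings are tempting. A reader might infer that precision is being given away at no cost. The logistic results show otherwise, since odds-ratio intervals become slightly wider. A reader might also infer that the primary analysis is underpowered or would gain power. It already exceeds its stated power, and the unadjusted Cochran-Armitage test stays primary, so its power does not change.

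**Conclusion.** The point holds as a cheap improvement. Baseline CRN stage is constant by design, finer baseline fibrosis measures are needed for other endpoints anyway, and no planned responder analysis adjusts for them. The case is clearest where the covariate is the endpoint's own baseline (Ishak improvement, CPA decrease), because SAP 6.4 already adjusts that way in its exploratory repeated-measures model.

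The benefit is correction of chance imbalance in the supportive odds ratios, plus a small power gain in that model: about 0 if Ishak is not prognostic, under 0.5 point at OR 2 and about 1 to 2.5 points at OR 4. These sizes rest on an assumed even Ishak split, the assumed prognostic odds ratios and, for fibrosis improvement, assumed response rates. The documents do not support a claim of bias, of inflated type I error or of a shortfall in the primary test.

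**What to change.** In SAP 6.1.1.1, and by reference in 6.1.2, extend the logistic model as follows:
- Primary endpoint, CRN improvement and Ishak improvement: add baseline modified Ishak (≤ 3 against ≥ 4).
- CPA decrease: add baseline CPA.
- Use one added covariate per endpoint. Do not extend the adjustment to progression to cirrhosis if events are sparse.
- Keep participants with a missing or unreadable baseline value, through a missing-indicator category or simple imputation, so that the mITT population is preserved.
- Report the adjusted odds ratio of each dose to placebo as supportive, next to the planned unadjusted ones.
- Leave the unadjusted Cochran-Armitage test as the primary analysis.

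The cost is a few lines of SAP text and one model run per endpoint, with no new data collection. The downside is one more term in models with few events and a slightly wider odds-ratio interval. The covariates should be fixed before the Week 24 unblinding, so that their choice cannot be seen as data-driven.
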